3.2 General study level definitions

3.2.1 Analysis timepoints

3.2.1.1 Relative day

Relative day for an event will be derived with the date of the first sc injection of IMP as reference.

Relative days for an event of measurement occurring before the date of first sc injection are calculated as follows:

$$\text{Relative Day} = \text{Event Date} - \text{Date of First Injection} \quad [1]$$

The relative day for an event or measurement occurring on or after the reference date to the date of the last injection is calculated as follows:

$$\text{Relative Day} = (\text{Event Date} - \text{Date of First Injection}) + 1 \quad [2]$$

For events or measurements occurring after the date of the last injection, relative day will be prefixed with '+' in the data listings and will be calculated as follows:

$$\text{Relative Day} = \text{Event Date} - \text{Date of Last Injection} \quad [3]$$

There is no relative Day 0. Relative day is not calculated for partial dates in cases where relative day is shown in a subject data listing. In such cases, relative day should be presented as '-' in the subject data listings.

3.2.1.2 Study periods

For each subject, the study will last a maximum of up to 40 weeks. This includes the following study period durations:

- Screening Period: up to 4 weeks
- Treatment Period: 28 weeks
- Safety Follow-Up Period: a SFU Visit is planned 20 weeks after the last dose of study medication

The end of the study is defined as the date of the last visit of the last subject in the study.

Additional analysis periods for classification of concomitant medications and AEs are provided in [Section 6.5.4](#) and [Section 11.2.1](#) respectively.

3.3 Definition of Baseline values

Baseline will be the last available value prior to the first injection of IMP. Scheduled or unscheduled measurements can be used as the Baseline value. Measurement-specific Baseline timepoints (based on the planned timepoints in the protocol) are presented in [Table 3–1](#).

Table 3–1: Definition of Baseline

Category	Measurement	Definition of Baseline
Efficacy	PASI IGA BSA HADS	Baseline Visit, or if missing the Screening results.
Pharmacodynamic	Mononuclear cell subtypes (flow cytometry)	Baseline Visit
Safety	Laboratory results (including hematology, biochemistry and urinalysis) Vital signs ECG Body weight C-SSRS	Baseline visit, or if missing the Screening results. For the C-SSRS the ‘Baseline’ version of the questionnaire will be completed at Screening and the ‘Since Last Visit’ version will be completed at all subsequent visits.
Immunological	ADA	Baseline Visit

ADA=anti-bimekizumab antibody; BSA=body surface area; C-SSRS=Columbia Suicide Severity Rating Scale; ECG=electrocardiogram; HADS=Hospital Anxiety and Depression Scale; IGA=Investigator’s Global Assessment; PASI=Psoriasis Area and Severity Index.

If a measurement is repeated at Baseline and is obtained prior to receiving the first dose of IMP, then the last available measurement will be used as the Baseline value.

3.4 Protocol deviations

Important protocol deviations are deviations from the protocol which potentially could have a meaningful impact on study conduct or on the primary efficacy, key safety, or PK/PD outcomes

for an individual subject. The criteria for identifying such protocol deviations will be defined within the protocol deviation specifications document which is part of the data cleaning plan. Important protocol deviations will include the following categories:

- Inclusion/exclusion criteria deviations
- Administration of prohibited concomitant medications
- Deviations relating to withdrawal criteria
- Visit schedule deviations
- Study drug administration deviations (including incorrect treatment received)
- Missing data

Important protocol deviations will be reviewed as part of the ongoing data cleaning process and data evaluation.

After all data have been verified/coded/entered into the database, the final data evaluation meeting (DEM) will be performed. The purpose of this DEM will be to review all protocol deviations, define the analysis sets and check the quality of the data prior to unblinding. The review will also help decide how to manage problems in the subjects' data (eg, missing values and withdrawals).

After the pre-analysis review, resolution of all issues, and documentation of all decisions, the database will be locked.

3.5 Analysis sets

3.5.1 Enrolled Set

The Enrolled Set (ES) will consist of all subjects who have given informed consent (ie, all screened subjects). This will therefore include screening failures.

3.5.2 Randomized Set

The Randomized Set (RS) will consist of all randomized subjects.

3.5.3 Safety Set

The Safety Set (SS) will consist of all subjects who received at least 1 dose of the study medication.

3.5.4 Full Analysis Set

The Full Analysis Set (FAS) will consist of all randomized subjects who received at least 1 dose of the study medication and have a valid measurement of the primary efficacy variable at Baseline.

3.5.5 Per-Protocol Set

The Per-Protocol Set (PPS) will consist of all randomized subjects who received at least 1 dose of the study medication and have a valid measurement of the primary efficacy variable post-Baseline without important protocol deviations affecting the measurement.

The analyses of the efficacy variables will be repeated for the PPS where stated in the SAP. If the FAS and PPS are the same, any outputs based on the PPS will not be presented.

3.5.6 Pharmacokinetics Per-Protocol Set

The Pharmacokinetics Per-Protocol Set (PK-PPS) will consist of all randomized subjects who received at least 1 dose of the study medication and provided at least 1 quantifiable plasma concentration post-dose.

3.5.7 Pharmacodynamics Per-Protocol Set

The Pharmacodynamics Per-Protocol Set (PD-PPS) will consist of all randomized subjects who received at least 1 dose of the study medication and provided at least 1 PD measurement post-dose without important protocol deviations affecting the measurement.

3.6 Treatment assignment and treatment groups

Treatment assignment for the SS, PK-PPS and PD-PPS will be according to the actual treatment received. Analyses of efficacy data (based on the FAS) will be conducted according to the randomized treatment.

Subjects receiving the incorrect treatment at a particular visit will be excluded from the PPS as this would be considered as an important protocol deviation. Subjects may be excluded from the analysis at a particular visit (or visits) only, following discussion at the DEM.

Listings and summaries will be presented by treatment group and overall where applicable (Table 14-1).

The following order will be used in the TFLs:

- Not randomized
- BKZ 320mg + PBO (Treatment arm A)
- BKZ 320mg (Treatment arm B)
- All subjects

In the case of dosing administration errors during the Treatment Period, all statistical analyses of safety, PK and PD data will be conducted according to the actual treatment received with the following rules:

- Subjects randomized to Treatment arm A who received bimekizumab at Week 16 will be summarized together with subjects in Treatment arm B
- Subjects randomized to Treatment arm B who received placebo at Week 16 will be summarized together with subjects in Treatment arm A

Any other dosing errors will be discussed at the DEM and the decision regarding the inclusion into the relevant analyses will be documented as part of the DEM minutes.

3.7 Center pooling strategy

The data from different sites will be pooled for all analyses. There will be no stratification by site or country performed.

3.8 Coding dictionaries

Adverse events and medical history will be coded using the Medical Dictionary for Regulatory Activities (MedDRA[®]), Version 19.0.

Medications will be coded according to the World Health Organization Drug Dictionary (WHODD [September 2015]). Medical procedures will not be coded

3.9 Changes to protocol-defined analyses

In the clinical study protocol the definition of the FAS included all subjects with a valid measurement of the primary efficacy variable post-Baseline. However, this was adjusted to all subjects with a valid Baseline measurement for the primary efficacy variable in the SAP in order to comply with program standards and FDA requirements (ie, inclusion into the FAS is no longer dependent on availability of post-Baseline data).

According to the final clinical study protocol spaghetti plots of change from Baseline in PASI would be plotted for each subject over time. However as the PASI response is based on percentage change, it was deemed more appropriate to present the individual plots based on percentage change from Baseline.

The protocol stated that exposure at risk for defining treatment-emergence for treatment-emergent adverse events (TEAEs) would be cut off at the Week 16 visit (for subjects who complete through the Week 16 visit) or at 20 weeks (140 days) after the last administration of study treatment (for subjects that discontinue prior to the Week 16 visit). This was further stated to be done in order to provide a fair comparison across all subjects when comparing the incidence of TEAEs. In this SAP amendment it has been clarified that the definition of a TEAE is any AE with onset following the first administration of study medication until the final administration of study medication + 140 days (regardless of study discontinuation). In order to allow for direct comparison of the treatment groups with respect to incidence of TEAEs, prior to the point at which subjects are eligible to enter the extension study, it would be necessary to use a cut off at Week 20 (ie, the first point at which a subject may enter the extension study). This has also been clarified in the SAP amendment accordingly.

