11.2 Adverse events

11.2.1 Definitions and classification of adverse events

All AEs will be recorded in the CRF from informed consent until study completion or termination.

Adverse events with start date prior to the first administration of IMP are defined as pre-treatment AEs. A TEAE is defined as any AE with a start date/time at the time of or after the first administration of IMP up until the last received dose of IMP + 140 days (which covers the 20 week SFU Period). Adverse events occurring after this date will not be classified as TEAEs and will therefore be excluded from the summary tables.

Where dates are missing or partially missing, AEs will be assumed to be treatment-emergent, unless there is clear evidence to suggest that the AE started prior to dosing. Handling of missing dates/times for classification of AEs as TEAEs is described in Section 4.2.4.

In order to allow for a comparative period across all subjects, prior to the point at which subjects are eligible to enter the extension study, TEAEs will be classified as follows:

- **Treatment Period TEAEs:** all TEAEs with onset at the time of or after the first administration of IMP up until the Week 20 visit. Any TEAEs that occur on the date of the Week 20 visit will be included (ie, the cut off will be assumed to be at 23:59 hours on the date of Week 20). Such TEAEs will be designated as 'Treatment Period' TEAEs in the tabulations. Any subjects that withdraw prior to Week 20 will have Treatment Period TEAEs cut off at 140 days relative to the first dose (ie, equivalent to 20 weeks).
- **Post-Treatment Period TEAEs:** all TEAEs with onset after the Week 20 visit up until the last dose of IMP + 140 days will be designated as 'Post-Treatment' TEAEs in the tabulations. Thus, any tabulation including Post-Treatment TEAEs will include only those TEAEs for subjects not entering the extension study at all or those TEAEs for subjects who enter the extension study at a later visit. For subjects that withdraw prior to Week 20, Post-Treatment Period TEAEs are classified as those starting after 140 days relative to the first dose (ie, equivalent to 20 weeks).

For the EAIR and EAER tabulations the above classifications will not be applicable, as these summaries are, by definition, adjusted for the individual exposure at risk for each subject.

All AEs will be coded and categorized by intensity (mild/moderate/severe) and relationship to IMP (related/not related).

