11.2.2 Calculation of exposure adjusted incidence and event rates

The EAIR is defined as the number of subjects (n) with a specific TEAE adjusted for the exposure and will be scaled to 100 subject-years:

$$EAIR = 100 \times \frac{n}{\sum_{i=1}^N T_{Exp,i}} \quad [13]$$

In the above equation, N is the total number of subjects at risk (in each treatment group) and $T_{Exp,i}$ is the time at risk for subject i , expressed in years. Subject time at risk represents the time a subject was at risk for having a TEAE calculated as follows:

- For subjects experiencing the specific TEAE the time at risk ($T_{Exp,i}$) is calculated from the time of the first dose to the onset of the TEAE. If a subject has multiple events, the time at risk is calculated relative to the first occurrence of the TEAE being considered.
- For subjects who do not experience the specific TEAE the total time at risk ($T_{Exp,i}$) is calculated as described in [Section 11.1.3](#).

Exact Poisson 95% CIs (lower confidence limit [LCL], upper confidence limit [UCL]) for the EAIR will be calculated using the relationship between the Poisson and the chi-square distribution (Fay and Feuer, 1997):

$$LCL = \frac{\chi_{2n, \frac{\alpha}{2}}^2}{2}, \quad UCL = \frac{\chi_{2(n+1), 1 - \frac{\alpha}{2}}^2}{2} \quad [14]$$

where n is the number of subjects with the specific TEAE for the incidence rate of interest and is the basis for the number of the degrees of freedom for the chi-square quantile. The LCL and UCL calculated above will be scaled to the number of subject-years by dividing these by the total exposure at risk for each treatment group ($\sum_{i=1}^N T_{Exp,i}$).

The EAER is defined as the total number of TEAEs (including repeat occurrences in individual subjects) divided by the total time at risk scaled to 100 subject-years:

$$EAER = 100 \times \frac{n_{AE}}{\sum_{i=1}^N T_{Risk,i}} \quad [15]$$

where n_{AE} is the total number of TEAEs and $T_{Risk,i}$ is the time at risk for subject i , expressed in years (calculated as described in [Section 11.1.3](#)).

No confidence intervals will be computed for EAER.

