11.2.3 Presentation of adverse events

An overview of the number and percentage of subjects who experience TEAEs will be presented by treatment group (including All Subjects), based on the SS. This tabulation will include the number and percentage of subjects with any TEAEs, serious TEAEs, related TEAEs, discontinuation due to TEAEs, severe TEAEs, AEs leading to death and TEAEs leading to death; event counts will also be included. The tabulation will be repeated for Treatment Period TEAEs and Overall TEAEs.

In addition, the following summaries will be presented by treatment group (including All Subjects), SOC, high level term (HLT) and PT, based on the SS:

- Incidence of TEAEs during Treatment Period
- Incidence of TEAEs Overall
- Incidence of serious TEAEs during Treatment Period
- Incidence of serious TEAEs Overall

-
- Incidence of non-serious TEAEs during Treatment Period
 - Incidence of non-serious TEAEs Overall
 - Incidence of TEAEs during Treatment Period by relationship
 - Incidence of TEAEs Overall by relationship
 - Incidence of TEAEs during Treatment Period by maximum relationship
 - Incidence of TEAEs Overall by maximum relationship
 - Incidence of TEAEs during Treatment Period by maximum intensity
 - Incidence of TEAEs Overall by maximum intensity
 - Incidence of fatal TEAEs during Treatment Period by relationship
 - Incidence of fatal TEAEs Overall by relationship
 - Incidence of non-serious TEAEs during Treatment Period by relationship
 - Incidence of non-serious TEAEs Overall by relationship
 - Incidence of serious TEAEs during Treatment Period by relationship
 - Incidence of serious TEAEs Overall by relationship
 - Incidence of non-serious TEAEs during Treatment Period above threshold of 5% of subjects
 - Incidence of non-serious TEAEs Overall above threshold of 5% of subjects
 - Incidence of non-serious TEAEs during Treatment Period above threshold of 5% of subjects by relationship
 - Incidence of non-serious TEAEs Overall above threshold of 5% of subjects by relationship
 - Incidence of TEAEs during Treatment Period by SOC and PT (including the number and percentage of subjects and individual subject numbers/reported terms for each PT stratified by intensity, relationship and seriousness)
 - Incidence of TEAEs (including all TEAEs during Treatment and Post-Treatment Periods) by SOC, HLT and PT and including the EAIR and EAER calculated as described in [Section 11.2.2](#)

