 - Incidence of TEAEs (including all TEAEs during Treatment and Post-Treatment Periods) by SOC, HLT and PT and including the EAIR and EAER, stratified by overall ADA status (positive/negative)

In addition, separate AE summaries by treatment group, SOC, HLT and PT (including all TEAEs during Treatment and Post-Treatment Periods combined) will be included for the following AEs of special monitoring (AESM):

- Major cardiovascular events
- Serious infections, including opportunistic infections and tuberculosis (TB)
- Malignancies including lymphoma

- Cytopenias
- Neuropsychiatric events (in particular, depression and suicide)
- Inflammatory bowel disease
- Anaphylactic reaction (hypersensitivity and anaphylactic reactions)
- Hepatic events and drug-induced liver injury

All summary tables (including those for AESM) will contain the number and percentage of subjects and the number of events where applicable. A subject who has multiple events in the same SOC, HLT and PT will be counted only once in the subject counts but all events will be included. In addition, for all tabulations of AESM, the EAER and EAIR will be reported.

The criteria for identifying AESM and additional criteria for reporting AESM are provided in [Section 14.6](#).

In summaries including relationship to IMP, the following relationship categories will be included:

- Related
- Not related

Subjects who experience the same event multiple times will be included in the most related category for tabulations by maximum relationship. Events with missing relationship will be considered as 'Related' for summary purposes but shown as missing in the data listings.

In summaries including intensity, the following categories will be summarized:

- Mild
- Moderate
- Severe

Subjects who experience the same event multiple times will be included in the most severe category for tabulations by maximum intensity. Events with missing intensity will be considered as severe for summary purposes. All data will be presented as recorded in the database for the listings.

Adverse event summaries will be ordered by alphabetical SOC, alphabetical HLT within SOC and decreasing frequency of PT in the 'BKZ 320mg' (Treatment arm B) column for tables including event counts. For tables including only number and percentage of subjects, summaries will be ordered by alphabetical SOC, alphabetical HLT within SOC and decreasing incidence of PT within HLT and SOC in the 'BKZ 320mg' (Treatment arm B) column.

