14.6.7 Anaphylactic reaction

Anaphylactic reactions will be summarized together in a stand-alone table with the following incidence rows:

- The first row within the body of the table will be labeled ‘Any hypersensitivity/anaphylactic reaction’ and will represent the overall incidence of subjects who reported at least one hypersensitivity reaction or at least one anaphylactic reaction.
- The second row within the body of the table will be labeled ‘Any hypersensitivity reaction’ and will represent the overall incidence of subjects who reported at least one hypersensitivity reaction.
- The third row within the body of the table will be labeled ‘Any anaphylactic reaction’ and will represent the overall incidence of subjects who reported at least one anaphylactic reaction.

Following these three overall incidence rows, all TEAEs that have been identified as either a hypersensitivity reaction or an anaphylactic reaction will be summarized by SOC, HLT and PT (these will not be presented by subcategory).

Hypersensitivity reactions and anaphylactic reactions will be identified as follows:

- **Hypersensitivity reactions:** all TEAEs with onset (start date/time) within 24 hours after any administration of IMP, which code to a PT which contains the term ‘hypersensitivity’ will be considered to be a hypersensitivity reaction and included in the summary table
- **Anaphylactic reactions:** An algorithmic approach will be used to identify TEAEs that are considered to be anaphylactic reactions. Preferred terms are separated into 4 distinct categories (A, B, C, D) prior to the algorithmic approach being applied.

All TEAEs with onset (start date/time) within 24 hours after any administration of IMP, and which fulfill any of the 3 criteria described in [Section 14.6.7.1](#) will be included in the summary table.

Any TEAEs with missing start time will be assumed to have occurred at the time of or after dosing for this purpose, if the event date is on the same day as a dosing date.

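### No AE summary table in this SAP starts at the Week 16 dose, where the arms first differ; 80% of the Week 0-20 comparison window is identical treatment

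*SAP*

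**What the plan says.** Protocol 5.4 and SAP 2.3 give both arms bimekizumab 320 mg at Baseline and Week 4. The arms part only at Week 16, when arm A receives placebo and arm B a third active dose. About 30 and 15 subjects are planned.

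Protocol 14.3.3.1 cut off exposure for the TEAE comparison at the Week 16 visit. SAP 3.9 replaces this with Week 20, the first point of entry to the extension, to allow "direct comparison of the treatment groups with respect to incidence of TEAEs, prior to the point at which subjects are eligible to enter" that study. SAP 11.2.1 then defines Treatment Period TEAEs as "all TEAEs with onset at the time of or after the first administration of IMP up until the Week 20 visit".

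The AE tables in SAP 11.2.3 use two windows:
- For the overview table, "The tabulation will be repeated for Treatment Period TEAEs and Overall TEAEs"; the incidence tables follow the same pair.
- Overall runs from first dose to last dose plus 140 days.

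The remaining AE summaries also begin at first dose:
- For subjects with the event, time at risk in the exposure-adjusted incidence rate (EAIR) is "calculated from the time of the first dose to the onset of the TEAE". For other subjects, and for the event rate (EAER), SAP 11.1.3 also counts from first dose.
- Tables of adverse events of special monitoring are produced "including all TEAEs during Treatment and Post-Treatment Periods combined".
- The hypersensitivity and anaphylaxis table takes events with "onset (start date/time) within 24 hours after any administration of IMP", which pools the three dosing visits.

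A Post-Treatment class is defined, but it starts after Week 20 and no stand-alone table of it is listed.

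**The concern.** The only contrast that randomization creates begins at the Week 16 injection. A reader who compares the two columns of a Week 0-20 table is looking mostly at time when the treatments were the same. With 15 subjects in arm B, a few chance differences from the first 16 weeks can hide or imitate an effect of the third dose. AE incidence is the primary safety variable (Protocol 4.1.4, SAP 2.2.1.4), so this is where a by-arm summary after the arms diverge would help most. No decision rule depends on it: what is at stake is how the safety tables are read.

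**Working it through.** **1. The plan's own figure.** SAP 11.2.1 equates 20 weeks with 140 days: 20 × 7 = 140. The Week 16 dose falls at 16 × 7 = 112 days.

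**2. Share of each window that is identical treatment.** Share = days to Week 16 dose ÷ days to end of window. The ±3-day windows (Protocol Table 5-1, footnote a) put Week 16 at 109-115 days and Week 20 at 137-143 days.

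| Window | Calculation | Identical share |
|---|---|---|
| Protocol cut-off, Week 16 | 112/112 | 100% |
| Treatment Period, nominal | 112/140 | 80% |
| Treatment Period, lowest | 109/143 | 76% |
| Treatment Period, highest | 115/137 | 84% |
| Overall, full follow-up (112 + 140 = 252 days) | 112/252 | 44% |
| Overall, subject leaves at Week 28 | 112/196 | 57% |
| Overall, subject leaves at Week 24 | 112/168 | 67% |

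A subject who leaves at Week 20 is back at 80%.

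**3. Dilution of a ratio.** Assume a constant background rate, uncommon events, and a true doubling in arm B after Week 16. The apparent ratio to week T is (16 + 2(T − 16))/T. It is 24/20 = 1.20 at Week 20, 32/24 = 1.33 at Week 24, 40/28 = 1.43 at Week 28 and 56/36 = 1.56 at Week 36.

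**4. Dilution of a risk difference.** The rates are assumed, since the documents give none, and early and late events are taken as independent. Cumulative incidence = 1 − (1 − p16)(1 − p4), where p16 is incidence by Week 16 and p4 is incidence over Weeks 16-20. SE = √(pA(1 − pA)/30 + pB(1 − pB)/15).

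| Assumed p16; p4 in A vs B | Gap, Weeks 16-20 (SE), points | Gap, Weeks 0-20 (SE), points | Gap/SE, 16-20 vs 0-20 |
|---|---|---|---|
| 8%; 2% vs 4% | 2.0 (5.7) | 11.68 − 9.84 = 1.84 (9.9) | 0.35 vs 0.19 |
| 40%; 20% vs 40% | 20 (14.6) | 64 − 52 = 12 (15.4) | 1.37 vs 0.78 |
| 70%; 20% vs 40% | 20 (14.6) | 82 − 76 = 6 (12.6) | 1.37 vs 0.48 |

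Gap/SE is 1.8 to 2.9 times higher from Week 16, but never above 1.4 in either table. For uncommon events the gap itself hardly shrinks; what grows is the noise around it.

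**5. Precision of a Week 16-20 table.** Subject-years are 30 × 28/365.25 = 2.30 in arm A and 15 × 28/365.25 = 1.15 in arm B. With windows the interval is 22-34 days, giving 1.8-2.8 and 0.9-1.4. One arm B subject is 1/15 = 6.7 points. As an example, 6/15 against 6/30 differs by 20 points, with a Newcombe 95% interval of about −7 to +46.

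**The case against.** The strongest reply is that nothing here is defective. The safety objective is to assess safety and tolerability, not to estimate a third-dose effect. SAP 2.4 says the study is not powered for safety. SAP 3.9 asks for comparability before extension entry, and Week 20 delivers it. It also adds the only differing exposure, because under the protocol's cut-off there was none. All of that stands, and it is why this is an optional improvement.

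Other safety data already show the arms after Week 16. SAP 11.3 tabulates markedly abnormal laboratory results by arm and visit, and SAP 11.4.1 does the same for vital signs. That stands, and it narrows the gap to AE summaries.

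The new table would also be weak: a post-randomization subset, few subject-years, and an arm A that may still carry drug from Weeks 0 and 4. That stands too, and the table should be labelled accordingly.

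Four stronger readings are tempting, but the documents do not support them:
- **Most events precede the dose that distinguishes the columns.** No event timing is given. The inference needs a constant rate, and even then fails for the Overall tables with full follow-up, where 56% of the time is after Week 16.
- **The Week 16 injection defines every subject's safety column.** SAP 3.6 does say "Subjects randomized to Treatment arm A who received bimekizumab at Week 16 will be summarized together with subjects in Treatment arm B", but as a rule for dosing errors. It does not sort subjects who never reach Week 16.
- **The information cannot be recovered.** One Treatment Period table gives "individual subject numbers/reported terms for each PT stratified by intensity, relationship and seriousness". The AE listings show time since the most recent dose (SAP 11.2.3), and visit dates, injection dates and days at risk are listed (SAP 5.1, 11.1.1, 11.1.3). For about 45 subjects, numerators and denominators can be rebuilt by hand.
- **No such table is planned anywhere.** SAP 4.5.1 and 4.5.2 refer to a DMC SAP and an interim SAP, neither of which was available.

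**Conclusion.** The point holds for this SAP and for AE summary tables only. None starts at the Week 16 dose, and the window chosen for comparing the arms is 80% identical treatment (76-84%). The Overall tables are about 44% identical with full follow-up and more for early leavers, and they lose the equal follow-up that the Week 20 cut-off secures. The time shares are calendar arithmetic and need no assumption about event rates. The dilution figures do rest on assumed rates: on those, a doubling reads as 1.20 over Weeks 0-20, and a 20-point gap in a broad row reads as 12 or 6 points. This is a gap in presentation, of low severity. Neither the existing window nor the added table can support a formal test.

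**What to change.** In SAP 11.2.1 to 11.2.3, keep every existing table and make three additions.

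1. One supportive, descriptive table of TEAEs with onset at or after the Week 16 injection, by arm, among subjects given that injection (active or placebo), as incidence to the Week 20 visit.
2. A rule for partial onset dates that could fall on either side of the Week 16 dose. Under SAP 4.2.4, a month-only date in that month is set to the 1st, which usually puts the event before the dose.
3. A footnote on the Week 0-20 tables saying that most of the window is identical treatment.

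Optionally, add EAIR and EAER with the clock and the first occurrence counted from the Week 16 dose, ending at the earlier of last contact (SAP 11.1.3, which already covers extension entry) and that dose plus 140 days. Label these rates as affected by extension entry after Week 20.

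The cost is one table, a short date rule and a footnote, using dates already collected; the optional rates bring a second window. The table leaves out subjects without a Week 16 injection. Incidence to Week 20 covers only about one half-life after the third dose (about 28 days, Protocol 2.2.1).
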